Secondary performance outcomes include the feasibility of inducing, maintaining, and rewarming patients from targeted temperature management using the Esophageal Cooling Device. Specifically, cooling rate, rewarming rate, and the percent of time during the goal-temperature maintenance period within 1°C of goal temperature (typically 33°C, but with some centers using anywhere from 32°C to 36°C) will be measured.

Secondary safety outcomes include evaluation of adverse events including the following: cardiac arrhythmias, severe bradycardia, myocardial infarction/re-infarction, dysphagia, odynophagia, aspiration pneumonia, non-aspiration pneumonia, reflux, esophageal injury, and esophagitis.

Specific definitions of adverse events and the methods used to identify and diagnose each during the treatment and 30-day follow-up phases are as follows:

- Cardiac arrhythmias - recording of atrial or ventricular arrhythmias during course of treatment.
- Severe bradycardia - heart rate < 30/min and necessitating pacing and cessation of TH.
- Myocardial infarction - universal definition of myocardial infarction as per the joint ESC/ACCF/AHA/WHF Task Force for the Redefinition of Myocardial Infarction.[50]
- Dysphagia - report from patient of difficulty in swallowing for more than 24 hours after cessation of device use, diagnosed with a Modified Barium Swallow Study, Videofluoroscopic Swallow Study, or patient self-report.
- Odynophagia - report from patient of pain with swallowing for more than 24 hours after cessation of device use, diagnosed by subjective patient sensation.
- Aspiration pneumonia - demonstration by chest X-ray of evidence of aspiration pneumonia, as diagnosed by treating physician, within 24 hours of cessation of device use.

- Non-aspiration pneumonia - demonstration by chest X-ray of evidence of pneumonia within 24 hours of cessation of device use that is diagnosed by the treating physician as non-aspiration pneumonia.
- Reflux - report of symptoms from patient within 3 days of recovery, with diagnosis via esophageal pH monitoring or endoscopy.
- Esophageal injury - evidence of traumatic and/or ischemic esophageal injuries diagnosed by gastroenterologist evaluation via esophagogastroduodenoscopy as warranted or indicated, and describing the absence of necrosis or not according to the Zargar classification used for caustic injuries within 3 days of recovery .

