- Esophagitis - evidence of esophageal inflammation diagnosed by gastroenterologist evaluation via esophagogastroduodenoscopy if warranted or indicated, and as defined by Savary-Miller and staged from 1 to 4 according to the severity of the disease within 3 days of recovery.

A serious adverse event (SAE) is defined as any adverse event that:

- Results in death
- Is life threatening
- Requires hospitalization or prolongation of existing hospitalization
- Results in persistent or significant disability or incapacity
- Is a congenital abnormality or birth defect

Patient population:

Patient population will consist of 15 patients suffering from traumatic brain injury, in whom the treating clinician has determined that targeted temperature management will be initiated.

Duration of patient's participation in the study

The patient's duration of the participation should be considered as follows:

- From signing of consent form by patient's legal representative and until 30 days if the patient has recovered within 30 days from the consent's signature and is able to sign the ICF personally;
- From signing of consent form by patient's legal representative and until the patient's recovery – patient's ability to sign the consent form (either a full or at least sufficiently partial neurologic recovery that allows the patient to awaken, function, understand conversation, ability to sign personally);
- From signing of consent form by patient's legal representative to patient's death

Inclusion criteria:

Adult patients (age 18 years and over)

Exclusion criteria:

- Patients with known esophageal deformity or evidence of esophageal trauma (for example, known esophageal varices, cirrhosis, history of esophagectomy, previous swallowing disorders, achalasia, etc.).
- Patients with known ingestion of acidic or caustic poisons within the prior 24 hours.
- Patients with less than 40 kg of body mass.
- Patients known to be pregnant.
- Terminal disease or “do not resuscitate order” that could lead to early-onset therapeutic withdrawal (<48 hours after collapse).
- Unstable hemodynamic conditions (defined as intractable severe cardiogenic shock or ECLS requiring) that could lead to multi-organ failure and early-onset death (<48 hours after collapse).
- Pre-existing severe conductive disorder requiring pacing.

Informed consent and ethical considerations:

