After the first 24 hours from the admission of the patient to the hospital Simplified Acute Physiology Score (SAPS) III will be measured.

Daily during day 1-7 if ICU stay the following procedures and assessments will be performed and recorded in the CRFs:

- Sequential Organ Failure Assessment (SOFA) scores;
- GCS scores;
- Pupillary and corneal reflex check;
- Highest body temperature;
- Highest dose and type of vasopressor/inotropic medication;
- The need for pacing;
- Intracranial pressure monitor pressures will be recorded (if measured);
- Recording of a need for mechanical circulatory assistance;
- Mechanical ventilation (if necessary);
- Recording of daily net fluid balance;
- Recording of adverse events;

Daily from day 8 to ICU discharge or day 14 the following records will be made:

- Patient comatose (yes or no);
- Mechanical ventilation (yes or no);
- Renal replacement therapy (yes or no);
- Presence of pneumonia (aspiration/non-aspiration) and sepsis (yes or no)

CPC should be assessed and recorded daily with the last recording being either at discharge, or at the 30 day time point.

Daily from day 1 to day 14 “do not attempt resuscitation order” should be recorded in the CRFs.

Based on investigator’s discretion, the following procedures may be performed if a decision is being contemplated for withdrawal of patient care”:

- Results and time of SSEP, if performed (n20 present bilaterally/n20 present unilaterally/n20 absent);
- Results and time of EEG, if performed.

At ICU discharge or 30 days from admission the following procedures will be recorded if performed (only CPC and GCS are mandatory):

- EEG, MRI, CT (if performed)
- CPC and GCS;

- Esophagogastroduodenoscopy (if performed)

Throughout the entire study:

- Concomitant medications;
- Adverse events

Statistical analysis

Sample size for primary outcome is calculated with an assumption of time to initiate cooling being approximately 5 minutes, with standard deviation of 4 minutes for the esophageal cooling device, and 20 minutes, with standard deviation of 15 minutes, for alternative devices. A power of 80%, and alpha of 5%, yields a sample size of 14 patients (with an equivalent size of historical controls). Sample size for secondary outcome is calculated for a non-inferiority test against the

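### Reflux counts only when a pH study or endoscopy confirms it, and both tests are left to discretion, so the reflux count partly measures who was tested

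*Combined protocol and SAP*

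**What the plan says.** The Secondary outcomes section of the combined protocol and SAP names ten adverse events as safety outcomes and defines each. Three of them begin with something the patient reports:

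- Reflux: "report of symptoms from patient within 3 days of recovery, with diagnosis via esophageal pH monitoring or endoscopy".
- Odynophagia, for which the complaint is enough: "report from patient of pain with swallowing for more than 24 hours after cessation of device use, diagnosed by subjective patient sensation".
- Dysphagia, where the complaint is one of three accepted routes: "diagnosed with a Modified Barium Swallow Study, Videofluoroscopic Swallow Study, or patient self-report".

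Of the two tests that can confirm reflux, pH monitoring is mentioned only in the definition. Endoscopy appears in the definitions of esophageal injury and esophagitis, where it is discretionary (for esophagitis, "gastroenterologist evaluation via esophagogastroduodenoscopy if warranted or indicated"). It appears once more under Study assessments and procedures, in the list for ICU discharge or day 30, as "Esophagogastroduodenoscopy (if performed)". That list opens by saying that "the following procedures will be recorded if performed (only CPC and GCS are mandatory)".

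Adverse events are collected generically. The list for days 1 to 7 includes "Recording of adverse events", adverse events appear again in the list that applies throughout the study, and the Data collection section says that the side effects named earlier are recorded for the whole study. No rule says how to score a patient who has reflux symptoms but no test.

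**The concern.** A definition that needs both a symptom and a test works as a specific measure if symptomatic patients are tested. Where testing is discretionary, a low count can mean that reflux was rare or that few symptomatic patients were tested. The reported figure does not separate the two.

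Reflux is a named safety outcome of a device that sits in the esophagus, and safety is in the study's title. With 15 treated patients, two or three cases that fail the definition for want of a test would change how the result reads.

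**Working it through.** **1. The three symptom-led definitions side by side.** Each starts from a patient's report, and they differ in what else is needed.

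| Outcome | Patient's report | Test also required? |
|---|---|---|
| Dysphagia | yes | no; self-report is one of three accepted routes |
| Odynophagia | yes | no; "diagnosed by subjective patient sensation" |
| Reflux | yes | yes; pH monitoring or endoscopy, no self-report route |

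**2. Where the confirming tests appear.** I checked the lists for screening, 0 to 39 hours, days 1 to 7, days 8 to 14, and ICU discharge or day 30. pH monitoring is in none of them. Endoscopy is only in the last, as an optional item.

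**3. The symptomatic, untested patient.** The first condition is met and the second is not, so the stated definition fails. The complaint can be entered as a general adverse event, but it is not a case of reflux as defined.

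**4. Range of the reported count.** The plan states no reflux rate, testing rate or reflux-specific power, so there is no figure to reproduce. Let S be the number symptomatic, T the number of those tested, and C the number confirmed. Then 0 ≤ C ≤ T ≤ S, and the plan reports C/15. Assume S = 4 for illustration (exact binomial 95% intervals):

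- T = 0, so C = 0: 0/15 = 0%, upper limit 1 − 0.025^(1/15) = 21.8%.
- T = 1, C = 1: 1/15 = 6.7% (0.2% to 31.9%).
- T = 4, C = 4: 4/15 = 26.7% (7.8% to 55.1%).

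A patient who is tested and found negative is properly left out of C. Only the S − T untested patients are lost to ascertainment, and the plan does not ask for S or T to be reported.

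**5. Sensitivity to ascertainment.** Let p be the true rate of symptomatic reflux, and f the fraction recorded as reflux, taken as (fraction elicited) × (fraction of those tested), assuming that a test in a true case confirms it. Then the expected count is 15pf and P(no case recorded) = (1 − pf)^15. With p = 0.20 assumed:

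| f | Expected count | P(no case recorded) |
|---|---|---|
| 1.00 | 15 × 0.20 × 1.00 = 3.0 | 0.80^15 = 0.035 |
| 0.25 | 15 × 0.20 × 0.25 = 0.75 | 0.95^15 = 0.46 |
| 0.10 | 15 × 0.20 × 0.10 = 0.30 | 0.98^15 = 0.74 |

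The documents do not fix f. Half elicited and 10% tested gives 0.5 × 0.10 = 0.05; half and half gives 0.25; 75% and 75% gives 0.56; full elicitation and testing gives 1.00.

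**The case against.** The best case for the plan has five parts.

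- **Objective confirmation is a legitimate choice.** Reflux symptoms are non-specific, and odynophagia, being pain, is subjective by nature and so an imperfect precedent. This stands as a reason to keep the confirmed measure. It is no reason to leave out the number tested.
- **A for-cause test need not be in a visit schedule.** The swallow studies for dysphagia are not scheduled either, and a symptomatic patient is a natural candidate for endoscopy. This also stands: the absence of a scheduled test is not in itself a defect. The difficulty is that the definition makes the test necessary, while nothing says that symptomatic patients will have one.
- **Adverse events are recorded throughout.** A reader might infer that no one is required to record esophageal symptoms, because only CPC and GCS are mandatory at the closing assessment. The documents do not support that. The restriction applies to the procedures in that list and not to adverse events, which have their own entry, and the Data collection section covers the named side effects, reflux among them. What remains is narrower: no listed item puts a specific question, and a recorded complaint without a test is still not reflux as defined.
- **The case report forms are not among the documents.** They may already contain esophageal symptom items. This cannot be settled here.
- **Nothing formal hangs on reflux.** It is one of ten secondary safety events, with no margin or test of its own. This limits the consequence to the descriptive safety message.

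**Conclusion.** The point holds in a limited form. Reflux is the only one of the three symptom-led outcomes that also needs a test, and the tests are discretionary. A symptomatic but untested patient fails the definition, so the count can be biased towards zero. This follows from the text alone.

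The size does not. The range from 0/15 to 4/15 rests on an assumed 4 symptomatic patients, and the probabilities on an assumed 20% rate and assumed recorded fractions. A reader might go further and infer that symptomatic reflux will usually be scored as no event. That needs f below one half, and the documents give neither an elicitation nor a testing rate; the assumed 75%/75% case gives 0.56, on the other side of that line.

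A related caution concerns comparison. The Statistical analysis section draws the historical controls for the secondary outcome from patients with endoscopy available, while treated patients have it only if performed. Ascertainment of endoscopy-based events may therefore differ between the groups. The documents do not say whether symptoms were recorded in the controls.

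**What to change.** Report reflux at two levels:

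- (a) patient-reported symptoms;
- (b) the subset confirmed by pH study or endoscopy, with the number tested as the denominator.

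This keeps the specific measure and shows how much testing lies behind it.

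Add three short questions, on reflux, difficulty swallowing and pain on swallowing, each with the answers yes, no and unable to answer. Put them at an existing contact within the 3 days of recovery that the definition already sets. Signing of the consent form by the recovered patient is one such contact if it falls in that window, since the section on duration of participation ties recovery to the ability to sign. Asking only at ICU discharge or day 30 would not do, because either may fall outside the window.

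The cost is the wording of one definition and three items on the case report form; no test or visit is added. The downside is that level (a) will include some non-specific symptoms and may have no counterpart in the historical controls. It should therefore be reported descriptively for the treated group and not used in a comparison.

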The aim of this prospective, interventional study is to assess the feasibility and safety of the Esophageal Cooling Device in 15 patients from the Ukraine suffering from traumatic brain injury who the treating physician is treating with targeted temperature management. Comparison of outcomes will be made to historical controls, and analysis will utilize a non-inferiority design. The primary outcome is the time to initiation of targeted temperature management, as measured from the time a decision is made to begin targeted temperature management, to the time the esophageal cooling device is in place. The secondary endpoints: the feasibility of inducing, maintaining, and rewarming patients from targeted temperature management using the Esophageal Cooling Device (cooling rate, rewarming rate, and the percent of time within goal temperature during the goal-temperature maintenance period); evaluation of adverse events (including cardiac arrhythmias, severe bradycardia, myocardial infarction/re-infarction, dysphagia, odynophagia, aspiration pneumonia, non-aspiration pneumonia, reflux, esophageal injury, and esophagitis) will be closely monitored during the whole period of targeted temperature management

Background:

Current medical practice entails modifying or influencing the temperature of patients for a large and growing number of conditions. For example, temperature control (which includes reduction of body temperature below normal, maintenance of normal body temperature for the avoidance of febrile or hyperthermic states by cooling, and active warming of patients to avoid unintended reductions of body temperature) has been shown either preliminarily or definitively to be beneficial for:

- patients who remain comatose after resuscitation from cardiac arrest[1-5]
- neonatal hypoxic ischemic encephalopathy[6-10]
- certain subsets of traumatic brain injury[11, 12]
- spinal cord injury[13-15]
- certain subsets of stroke[16-20]
- acute myocardial infarction[21-24]
- traumatic/hemorrhagic cardiac arrest[25]
- surgical operations lasting longer than 1 hour[26-31]
- hepatic encephalopathy[32-34]
- severe heat stroke[35, 36]
- sepsis/septic shock[37]

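### The esophageal injury and esophagitis definitions use a recovery-based window that is undefined for patients who die or stay comatose and conflicts with the stated treatment and 30-day ascertainment period

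*Combined protocol and SAP*

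**What the plan says.** The definitions stand under Secondary outcomes. Esophageal injury is "diagnosed by gastroenterologist evaluation via esophagogastroduodenoscopy as warranted or indicated", with necrosis noted as present or absent "according to the Zargar classification used for caustic injuries within 3 days of recovery". Esophagitis is also an endoscopic diagnosis, and its definition ends "staged from 1 to 4 according to the severity of the disease within 3 days of recovery".

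Recovery is described once, under Duration of patient's participation in the study: "either a full or at least sufficiently partial neurologic recovery that allows the patient to awaken", to the point of being able to sign consent in person. The same section provides for participation that ends in death.

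Other places set a wider period:

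- The lead-in to the list of definitions speaks of "the methods used to identify and diagnose each during the treatment and 30-day follow-up phases are as follows".
- The Abstract names esophageal injury and esophagitis among events that "will be closely monitored during the whole period of targeted temperature management".
- Data collection has the listed side effects recorded for the whole study.
- Study assessments and procedures records adverse events daily on days 1 to 7 in the ICU and throughout the study. It also records endoscopy, where done, at ICU discharge or 30 days from admission, with no reference to recovery.

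**The concern.** A recovery anchor makes sense for reflux, which starts from a symptom that the patient must report. It does not fit a lesion that a gastroenterologist sees at endoscopy, which can be found in a comatose patient. Other items in the list are tied to treatment or to the device. Arrhythmias are counted over the course of treatment, the two pneumonia items within 24 hours of stopping device use, and dysphagia and odynophagia by persistence beyond 24 hours after stopping. A device-based clock was therefore available and was used.

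Safety is half of the stated aim, and the device works by contact with the esophageal mucosa. If the window decides what counts, the two esophageal outcomes open at a time set by the brain injury and not by exposure to the device. The loss would fall mainly on patients who die or wake late, and some lesions could heal before a late waking.

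Statistical analysis also asks for historical controls who have an endoscopic evaluation, which suggests that esophageal findings are meant to be compared. No recovery window is stated for those controls. A literal window applied to the device patients alone could favour the device.

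**Working it through.** The plan gives no figure for this point, so the main check compares the texts. Two readings are possible:

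- **Literal:** a lesion counts if seen within 3 days of recovery.
- **Lead-in:** a lesion counts if seen during treatment or the 30-day follow-up.

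The days below are chosen only to show how each reading works.

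| Case | Literal | Lead-in |
|---|---|---|
| Lesion seen day 2, device in place; patient wakes day 20 (20 − 2 = 18 days before recovery) | Does not count | Counts |
| Lesion seen day 2; patient dies without waking | No recovery date, so undefined | Counts |
| Patient wakes the day after device removal; lesion seen that day | Counts | Counts |
| Patient wakes day 35; lesion seen that day | Counts | Outside 30 days |

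Neither reading contains the other, so the conflict cannot be settled by taking the wider one.

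**Illustration of size.** The documents give n = 15. The numbers of lesions and of patients who never recover are assumptions.

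- One uncounted lesion: 1/15 = 6.7 percentage points.
- Two lesions seen before recovery, counted: 2/15 = 13.3%, exact (Clopper-Pearson) 95% CI 1.7% to 40.5%.
- The same two not counted: 0/15, with upper limit 1 − 0.025^(1/15) = 21.8%.
- If 5 of 15 never recover (range 3 to 7, that is 3/15 = 20% to 7/15 = 47%), the window opens for 10 (range 12 to 8). Zero events then has an upper limit of 1 − 0.025^(1/10) = 30.8% (range 26.5% for 12 to 36.9% for 8), not 21.8%.
- With an assumed true lesion rate of 10%, the chance of seeing at least one lesion is 1 − 0.9^15 = 79% with all 15 assessable and 1 − 0.9^10 = 65% with 10.

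The zero-event limits and the chance of seeing a lesion also assume that every patient in the denominator is scoped. The plan does not require this, because endoscopy is done only when prompted. That is a separate limit on ascertainment.

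**The case against.** A reader might infer that the protocol excludes lesions found during device use, in coma or in patients who die. The documents do not say so. Neither definition contains the word *only* or any exclusion rule. The lead-in, the Abstract, Data collection and Study assessments and procedures all provide for monitoring or recording through treatment and beyond. A patient scoped on day 2 with necrosis would be recorded as having an adverse event, and a serious one if it was life-threatening or fatal.

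The wording also allows milder readings. In both definitions the phrase follows the grading clause, so it may time the grading and not limit what counts as an event. It does not say before or after recovery, so a lesion seen shortly before waking may qualify. The description of recovery was written for duration of participation, and carrying it into the safety definitions is an inference. The record of endoscopy at ICU discharge or 30 days is not a competing window; it supports capture of earlier findings. A reader might also call these the main safety outcomes, but the protocol lists them as two of ten unranked secondary safety events.

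All of this stands, and it rules out a claim of definite exclusion. It does not settle the outcome count. Recording an event does not decide whether it meets a definition, and a specific limit inside a definition can be read as overriding a general recording rule. If the phrase times only the grading, a lesion in a patient who never wakes has no grade within the protocol's window. Each reading leaves an edit to make.

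**Conclusion.** The recovery-based window is undefined for patients who die or stay comatose and conflicts with the ascertainment period stated in the lead-in to the same list. Lesions found earlier would probably be recorded as adverse events. Whether they count toward esophageal injury or esophagitis is open, and as the plan stands that could be decided after the data are seen. The downward bias is conditional on the literal reading, under which it is greatest in patients who die or wake late. The 0/15, 2/15 and 0/10 figures show scale under assumed inputs and are not estimates. The textual conflict does not depend on them. The two rates cannot be interpreted until the window is settled.

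**What to change.** In both definitions, replace the recovery window with: *at any time from device placement to the end of participation (day 30, recovery if later, or death)*. State that any lesion documented by clinically prompted endoscopy, or by autopsy if one is done, is counted and graded, whatever the patient's neurologic state. A plain cutoff at day 30 or death would not do, because it drops a lesion found when a patient wakes after day 30, which the present wording counts.

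Two details should be settled in the same edit. Day 30 needs one origin, since participation runs from consent while the assessment schedule counts from admission. If findings in the three days after a late recovery are to be kept, participation must extend to cover them.

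Record device removal time beside the placement time already collected, date each lesion relative to both, and report how many patients were scoped and when. Any comparison with historical controls should state the window used for them.

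The cost is two definition sentences, one case report form field and a possibly less favourable event rate. No endoscopy is added and no treatment changes.

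### Participation of late recoverers ends at recovery, so the 3-day window for patient-reported reflux goes unobserved, and survivors who never recover have no end date

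*Combined protocol and SAP*

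**What the plan says.** All references are to the combined protocol and SAP.

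*Duration of patient's participation in the study* gives three end points, each counted from the legal representative's signature:

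- The first keeps a patient in "until 30 days if the patient has recovered within 30 days" of consent and can sign personally.
- The second runs "until the patient's recovery", with no days added afterwards and no maximum. Recovery is explained there as "either a full or at least sufficiently partial neurologic recovery that allows the patient to awaken, function, understand conversation, ability to sign personally". This is the only definition of recovery in the document.
- The third reads "From signing of consent form by patient's legal representative to patient's death".

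The adverse-event definitions under *Secondary outcomes* tie three outcomes to recovery:

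- Reflux: "report of symptoms from patient within 3 days of recovery", confirmed by pH monitoring or endoscopy.
- Esophageal injury: endoscopic findings graded "according to the Zargar classification used for caustic injuries within 3 days of recovery".
- Esophagitis: endoscopic findings "staged from 1 to 4 according to the severity of the disease within 3 days of recovery".

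The same section speaks of a 30-day follow-up phase for adverse events. *Study assessments and procedures* places the last CPC score at discharge or day 30, and the final assessment "At ICU discharge or 30 days from admission". Adverse events are to be recorded for the whole study, whose length is not defined anywhere except in the participation section.

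**The concern.** The second end point closes participation at the event that opens the reflux window. A patient who regains the ability to sign after day 30 leaves the study at that point, and the symptom report that defines reflux is due in the 3 days that follow. A patient who recovers in the last days before day 30 loses part of the window. A survivor who never regains the ability to sign meets none of the three end points, although the rest of the protocol works to a 30-day horizon.

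This is a feasibility and safety study of a device placed in the esophagus, so these outcomes bear directly on possible device harm. The loss of observation depends on neurologic outcome and falls on the slowest-recovering survivors. The *Statistical analysis* section does not say how a patient with an unobserved safety outcome is to be handled, so such a patient could be counted as event-free. Each patient is 1/15 = 6.7% of the sample.

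**Working it through.** There is no stated figure to reproduce, so the check is a timeline.

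**Inputs.** Let R be the day of recovery, in elapsed days from consent.

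- End of participation E, from the participation section: E = 30 if R ≤ 30, and E = R if R > 30. The second case is inferred by contrast with the first end point, because the second does not itself mention day 30.
- Reflux window, from the adverse-event definition: R to R + 3, taken as running forward from recovery.

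**Formula.** Window days inside participation = max(0, min(E, R + 3) − R).

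| Recovery day R | End E | Window | Days observed |
|---|---|---|---|
| 5 | 30 | 5–8 | 8 − 5 = 3 |
| 20 | 30 | 20–23 | 23 − 20 = 3 |
| 27 | 30 | 27–30 | 30 − 27 = 3 |
| 28 | 30 | 28–31 | 30 − 28 = 2 |
| 29 | 30 | 29–32 | 30 − 29 = 1 |
| 30 | 30 | 30–33 | 30 − 30 = 0 |
| 31 | 31 | 31–34 | 31 − 31 = 0 |
| 60 | 60 | 60–63 | 60 − 60 = 0 |

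Recovery up to day 27 gives the full window. From day 30 on, nothing is left. Counting the recovery day itself as the first window day would shift these figures by one day and leave the pattern the same.

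**The two endoscopic outcomes.** Their definitions need an endoscopy done when indicated. They need no patient report and no ability to sign. If the phrase about 3 days is read as covering days on either side of recovery, an endoscopy shortly before recovery falls both inside the window and inside participation. For these two outcomes the table is therefore a worst case.

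**Never recovered and alive.** The first and second end points require recovery and the third requires death, so no end date follows. The scheduled assessments nevertheless stop at discharge or day 30.

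**Time origin.** The participation section counts its 30 days from consent, while the final assessment counts them from admission. The two clocks need to be aligned when the sections are reconciled.

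**The case against.** The strongest reply is that this is mainly a matter of wording in secondary outcomes. Parts of it stand, and they rule out several stronger readings that a reader might infer.

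- *That all three esophageal outcomes become unobservable.* The text does not support this. Endoscopy can be done before recovery, and any result available at ICU discharge or day 30 is to be recorded. Only reflux, which needs an awake patient to report symptoms, depends in practice on time after recovery.
- *That adverse-event follow-up is too unequal for rates to be compared.* Counted from consent, early recoverers are followed to day 30 and later or non-recovering survivors beyond it. Every survivor has at least 30 days of adverse-event recording, so day-30 rates can already be reported. Nor can non-comparability with historical controls be traced to this rule, since the document describes no follow-up schedule for them.
- *That unobserved patients would be counted as event-free.* No section says so. The document is silent, which leaves it possible and no more.
- *That data collection never ends for the non-recovered.* Participation has no end date, but scheduled assessments stop. Only adverse-event and concomitant-medication recording runs on.
- *That a definite share of the sample is lost.* The document gives no recovery rate. Supposing 2 to 6 of 15 patients (2/15 = 13% to 6/15 = 40%) would be pure assumption. It would also pool late recoverers with those who never recover, for whom no follow-up rule can create a recovery window.

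It is also fair to say that the late-recoverer reading of the second end point is an inference, and that the adverse-event definitions do not themselves define recovery. The inference is the mild one: if the second end point applied to every recoverer, it would contradict the first outright and more patients would lose the window. None of this removes the gap for reflux or supplies the missing end date.

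**Conclusion.** The point holds in a limited form. Followed as written, the participation rule defeats the reflux definition for patients who recover on day 30 or later (0 of 3 days observed) and shortens the window for recovery on day 28 or 29 (2 or 1 days). Esophageal injury and esophagitis are affected only where no endoscopy precedes recovery. A survivor who never recovers has no end of participation, at odds with the 30-day horizon used elsewhere.

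This rests on three readings: the second end point means recovery after day 30, recovery in the adverse-event definitions has the meaning given in the participation section, and the reflux window runs forward. The number of patients affected is unknown and could be zero. Time to device placement, the primary outcome, is not touched. It is a real flaw in a secondary safety outcome and is cheap to correct.

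**What to change.** Reconcile the participation section, the adverse-event definitions and the assessment schedule with one rule, using one time origin:

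- Follow each patient to death or to the later of day 30 and 3 days after recovery.
- Set a fixed last-contact day, no earlier than day 30, for patients who have not recovered.
- State that recovery in the adverse-event definitions means what the participation section says, and whether the 3 days run forward only.
- Class patients whose recovery window was not observed as not evaluable for reflux. Do the same for esophageal injury and esophagitis unless an endoscopy result is available. Report the evaluable denominator beside each rate.
- Report other adverse events to day 30 for all patients, which the current wording already allows.

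The cost is protocol wording, one short contact for each late recoverer, and a smaller evaluable denominator for these outcomes. Patients who never recover gain a defined end of participation.
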